9.1.1. Adverse Events of Special Interest

There are no prespecified AEs of special interest (AESI) for this study.

9.2. Adverse Drug Reactions

Adverse drug reactions (ADR) (also known as suspected unexpected adverse drug reactions or SUSARs) are all noxious and unintended responses to a medicinal product related to any dose. The phrase “responses to a medicinal product” means that a causal relationship between a medicinal product and an adverse event is at least a reasonable possibility, i.e., the relationship cannot be ruled out. Therefore, a subset of AEs can be classified as suspected ADRs or SUSARs, if there is a causal relationship to the medicinal product.

9.3. Serious Adverse Events

A serious adverse event (SAE) is defined as an adverse event that meets any of the following criteria:

- Results in death.
- Is life threatening; that is, poses an immediate risk of death as the event occurred.
 - This serious criterion applies even if the participant, in the view of the Investigator or Sponsor, is at immediate risk of death from the AE as it occurs. It does not apply if an AE hypothetically might have caused death if it were more severe.
- Requires inpatient hospitalization or prolongation of existing hospitalization.
 - A participant admitted to a hospital, even if he/she is released on the same day, meets the criteria for the initial inpatient hospitalization. An emergency room visit that results in admission to the hospital would also qualify for the initial inpatient hospitalization criteria. However, emergency room visits that do not result in admission to the hospital would not qualify for this criteria and, instead, should be evaluated for 1 of the other criteria in the definition of serious (e.g., life threatening adverse experience, important medical event).

- Hospitalizations for reasons not associated with the occurrence of an AE (e.g., preplanned surgery or elective surgery for a pre-existing condition that has not worsened or manifested in an unusual or uncharacteristic manner) do not qualify for reporting.
 - For example, if a participant has a condition recorded on his/her medical history and later has a preplanned surgery for this condition, it is not appropriate to record the surgery or hospitalization as an SAE, since there is no AE upon which to assess the serious criteria.
 - Please note that, if the pre-existing condition has worsened or manifested in an unusual or uncharacteristic manner, this would then qualify as an AE and, if necessary, the seriousness of the event would need to be determined.
- Results in persistent or significant disability or incapacity.
 - This serious criterion applies if the “disability” caused by the reported AE results in a substantial disruption of the participant’s ability to carry out normal life functions.
- Results in a congenital anomaly or birth defect in the offspring of the participant (whether the participant is male or female).
- Is an important medical event that, based upon appropriate medical judgment, may jeopardize the participant and may require medical or surgical intervention to prevent 1 of the other outcomes listed in the definition of serious.
 - Examples of such medical events include allergic bronchospasm requiring intensive treatment in an emergency room or at home, blood dyscrasias that do not result in inpatient hospitalization, or the development of drug dependency or drug abuse.

9.4. Reporting and Recording AEs

The Investigator will carefully monitor each participant throughout the study for possible AEs. In order to ensure complete safety data collection, all AEs occurring during the study (i.e., after the signing of the Informed Consent form), including the pre-treatment period required by the protocol, must be reported in the CRF even if no IMP was taken but specific study procedures were conducted. This includes all AEs not present prior to the initial visit and all AEs that recurred or worsened after the initial visit.

All AEs will be collected and reported in the electronic data capture (EDC) system and compiled into reports for periodic reviewing by the Medical Monitor. The Medical Monitor shall promptly review all information relevant to the safety of the investigational product, including all serious adverse events (SAEs). Special attention will be paid to those that result in permanent discontinuation of the investigational product being studied, whether serious or non-serious.

If the investigator learns of any SAE, including a death, at any time after a participant has been discharged from the study, and he/she considers the event to be reasonably related to the IMP or study participation, the investigator must promptly notify the sponsor (or designee).

Serious AEs that occur more than 30 days after the last dose of IMP need not be reported unless the investigator considers them related to the IMP.

9.4.1. Assessment of AEs

Adverse events will be solicited in a consistent manner at every study visit. Participants will be asked uniform open-ended questions to elicit any medically related changes in their well-being. They will also be asked if they have been hospitalized, had any accidents, used any new medications, changed concomitant medication regimens (prescription or OTC medications), noticed any changes in bowel habits or had unplanned visits to their general practitioner since the last visit.

In addition to participant observations, AEs identified from any study data (e.g., laboratory values, physical examination findings, ECG changes) or identified from review of other documents (e.g., participant diaries) that are relevant to participant safety will be documented on the AE page in the CRF.

If the participants reports an adverse event, the following will be recorded in the source and on the eCRF:

1. Description of the event
2. Date and time of onset and resolution (duration)
3. Record grading as per appropriate toxicity scale
4. Seriousness (does the event meet the above definition for an SAE)
5. Causality, relation to investigational product
6. Action taken regarding investigational product
7. Outcome
8. If any Concomitant Medications were given
9. Whether the AE resulted in participant withdrawal from the study
10. Investigator-specified assessment if the AE is related to a recent/current COVID infection
11. If a COVID positive PCR test received within the last 14 days

Signs or symptoms of a participant's atopic dermatitis should be recorded as AEs only if their nature changes considerably or their frequency or intensity increases in a clinically significant manner as compared to the clinical profile known to the Investigator from the participant's history.

9.4.2. Assessment of Severity

The severity, or intensity, of an AE refers to the extent to which an AE affects the participant's daily activities or their health. The intensity of the AE will be rated in accordance with the CTCAE Version 5.0. Adverse events related to temperature and abnormal laboratory results that are not found in the CTCAE Version 5.0 will be rated in accordance with the FDA Guidance for Industry *Toxicity Grading Scale for Healthy Adult and Adolescent Volunteers Enrolled in Preventive Vaccine Clinical Trials* [[Appendix 14.5 Toxicity Grading Scale](#)].

Changes in the severity of an AE should be documented to allow an assessment of the duration of the event at each level of intensity to be performed. Adverse events characterized as intermittent do not require documentation of onset and duration of each episode.

9.4.3. Assessment of Causality

The investigator's assessment of an AE's relationship to IMP is part of the documentation process. Regardless of the investigator's assessment of an AE's relationship to IMP, the AE must be reported.

The relationship or association of the IMP in causing or contributing to the AE will be characterized using the following classification and criteria:

Unrelated: There is no association between the IMP and the reported events.

Possible: Treatment with the IMP may have caused or contributed to the AE, i.e., the event follows a reasonable temporal sequence from the time of drug administration or follows a known response pattern to the IMP but could also have been produced by another factor.

Probable: A reasonable temporal sequence of the event with drug administration exists and, based upon the known pharmacological action of the drug, known or previously reported adverse reactions to the drug or class of drugs, or judgment based on the investigator's clinical experience, the association of the event with the IMP seems likely. The event disappears or decreases on cessation or reduction of the dose of IMP.

Definite: A definite causal relationship exists between drug administration and the AE, and other conditions (concurrent illness, progression/expression of disease state, or concurrent medication reaction) do not appear to explain the event. The event reappears or worsens if the IMP is re-administered.

9.4.4. Description of Adverse Events

When recording an AE, the Investigator should use the overall diagnosis or syndrome using standard medical terminology, rather than recording individual symptoms or signs. The eCRF and source documents should be consistent. Any discrepancies between the participant's own words on his/her own records (e.g., diary card) and the corresponding medical terminology should be clarified in the source documentation.

Details for completion of the Adverse Event eCRF are described in the eCRF Completion Guidelines.

9.4.4.1. Rule for Repetition of an AE

An increase in the intensity of an AE should lead to the repetition of the AE being reported with:

- The outcome date of the first AE that is not related to the natural course of the disease being the same as the start date of the repeated AE, and the outcome of "worsening".
- The AE verbatim term being the same for the first and repeated AE, so that the repeated AE can be easily identified as the worsening of the first one.

9.5. Reporting Serious Adverse Events

Serious Adverse Events (SAEs) must be reported to the Medical Monitor and Sponsor immediately, without undue delay but no later than within 24 hours of the site learning of the SAE.

To report the SAE, the investigator must record the SAE on the AE eCRF in the EDC system as well as any relevant CRF forms (e.g., drug dispensation CRF, applicable laboratory CRF). When the AE CRF is completed, [REDACTED] personnel will be notified electronically automatically and will retrieve the form.

If the event meets serious criteria and it is not possible to access the EDC system, please complete the back-up paper SAE Form in English with as much information that is known at the time and send it by e-mail to [REDACTED], or call the [REDACTED] SAE hotline and fax the completed paper SAE Form to [REDACTED] immediately, without undue delay but no later than within 24 hours of awareness. When the EDC system becomes available, the SAE information must be entered within 24 hours of the system becoming available.

The Sponsor has the legal responsibility to notify both the local regulatory authority and other regulatory agencies about the safety of an IMP under clinical investigation. The Sponsor will comply with country-specific regulatory requirements relating to safety reporting to the regulatory authority, IRB/IEC, and Investigators.

An Investigator who receives a safety notification letter describing a SUSAR or other specific safety information from the Sponsor, will review and will notify the local IRB/IEC, if appropriate according to local requirements.

9.5.5. Follow Up of Adverse Events

All AEs must be followed to satisfactory resolution, until the Investigator deems the event to be chronic or not clinically significant, the event is considered stable, the participant dies, or the participant is lost to follow-up. However, any new AEs that start more than 28 days after the final dose and changes in AEs that occur after the participant's end of study visit will not be recorded in the eCRF.

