7.8. Week 20 Follow--Up Visit

This visit will take place 141 days (+3 days) after the Day 1 Visit. Prior to the visit, the participant will be asked to withhold the application of the emollient until after all study assessments have been performed. See [Section 6.9.1.1 Background Therapy](#).

The following procedures will be performed:

- Perform brief physical examination
- Measure vital signs including weight
- Perform 12-lead ECG
- Collect blood for safety labs as well as inflammatory markers
- Collect urine for urinalysis
- Perform urine pregnancy test for WOCBP
- Take digital photographs of the same body locations taken at the Day 1 Visit
- Perform AD rating scales, including vIGA, EASI (and BSA), and SCORAD
- Perform patient reported clinical rating scales – HADS, POEM, DLQI, ADCT, and SF-12
- Review and document concomitant medications and therapies including emollient use
- Assess and document adverse events (AEs)
- Assist the participant to uninstall the mobile application from their smartphone device

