10.2 Adverse Events

Adverse events will be reported from the date of signed informed consent and through the Week 16 visit for participants entering the OLE study/28 days after cessation of dosing for participants who don't enter OLE. Adverse events occurring after the 28 days post-treatment would only be reported if the investigator considers it to be related to the study treatment.

Only treatment emergent AEs (TEAEs) will be included in the summaries, pre-treatment AEs will be included in the listings of all AEs.

All AEs will be coded using MedDRA. The dictionary will be updated through the life of the study with version 24.0 used initially. Severity of event will be coded using the Common Terminology Criteria for Adverse Events v5.0 (CTCAE).

An overview of TEAEs will be produced showing the number and percentage of participants with:

- Any TEAEs
- Any TEAE of CTCAE grade 2 or above
- Any TEAE of CTCAE grade 3 or above
- Any TEAE of CTCAE grade 4 or above
- Any fatal TEAE
- Any serious TEAE
- Any TEAE leading to permanent discontinuation of study drug
- Any TEAE leading to withdrawal from the study
- Any related TEAE
- Any related TEAE of CTCAE grade 2 or above
- Any related TEAE of CTCAE grade 3 or above
- Any related TEAE of CTCAE grade 4 or above
- Any related fatal TEAE
- Any related serious TEAE
- Any related TEAE leading to permanent discontinuation of study drug
- Any related TEAE leading to withdrawal from the study

Related events are those which were considered by the investigator to be possibly, probably or definitely related to study drug.

TEAEs will also be summarized by system organ class (SOC) and preferred term (PT). Summary tables will contain the number and percentage of participants and the number of events. A participant who has multiple events in the same SOC or the same preferred term will be counted only once in the participant counts but all events will be counted in the event counts. Adverse event summaries will be sorted by the internationally agreed SOC order ([Table 5](#)) and decreasing incidence of preferred term within SOC in the EDP1815 column.

Related TEAEs and TEAEs of CTCAE Grade 3 or above will also be summarized by SOC and PT in the same manner as described above.

Non-serious TEAEs will be also summarised by SOC and PT, however, PTs will be presented only in case of TEAEs reported by at least 5% of participants in any treatment group.

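### Section 9.5.5 bars new adverse events after day 28 from the eCRF, although SAEs to day 30 and later related SAEs are reportable and the eCRF is their recording route

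*Protocol*

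**What the plan says.** Four sections govern adverse events that start after treatment ends.

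- **Protocol 9.4** sets the SAE limit through an exemption: "Serious AEs that occur more than 30 days after the last dose of IMP need not be reported unless the investigator considers them related". It also requires prompt notification of the sponsor or designee when an investigator learns of an SAE "at any time after a participant has been discharged from the study" and considers it related to the product or to study participation. No form is named for that notification.
- **Protocol 9.5** fixes the recording route: "the investigator must record the SAE on the AE eCRF in the EDC system". The paper form is a back-up for when the EDC system cannot be reached, and its content must then be entered in the EDC.
- **Protocol 9.5.5** asks for AEs to be followed to resolution or stability. It then says that "any new AEs that start more than 28 days after the final dose", and changes in AEs after the end-of-study visit, "will not be recorded in the eCRF". Protocol 9.3 defines an SAE as a kind of AE, so the cut-off applies to SAEs too.
- **SAP 10.2**, for participants who do not enter the open-label extension, also draws its line at 28 days but lets related events through: "Adverse events occurring after the 28 days post-treatment would only be reported if the investigator considers it to be related".

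On the last contact, Protocol 7.8 times the final visit from Day 1: "This visit will take place 141 days (+3 days) after the Day 1 Visit". Protocol 7.9 times the early-termination call from the last dose, at 28 days (+3).

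**The concern.** A site that learns of an SAE starting on day 29 or 30 is told to report it, told to record it on the AE eCRF, and told that it will not be recorded in the eCRF. A related SAE after day 30 raises the same difficulty. What the site does depends on which section it opens first.

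The stake is the completeness of the serious-event data at the end of exposure. If sites follow 9.5.5, reportable SAEs drop out of the data behind the safety tables while the sponsor's safety function may hold them. The SAE reconciliation in Protocol 9.8 would then show mismatches that the protocol itself creates. SAP 5.3.4.2 counts AEs in the follow-up phase as treatment-emergent up to the participant's last day in the study, with no 28-day cap, so the analysis definition would accept events that the collection rule refuses. Protocol 9.9 halts the study on small counts of related SAEs, so their recording route should not be in doubt.

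**Working it through.** **Step 1: the rules side by side.** Days are counted from the last dose.

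| Event | Protocol 9.4 | Protocol 9.5 | Protocol 9.5.5 | SAP 10.2 |
|---|---|---|---|---|
| Unrelated SAE starting day 29–30 | Reportable | AE eCRF | Not in eCRF | Not reported |
| Related SAE starting day 29–30 | Reportable | AE eCRF | Not in eCRF | Reported |
| Related SAE starting after day 30 | Reportable; if learned of after discharge, notify sponsor, form not named | AE eCRF | Not in eCRF | Reported |
| Outcome of an SAE still ongoing at the end-of-study visit | No specific rule | No specific rule | Follow up, but do not record the change | No specific rule |

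No row with a new event has a single answer. The 30-day duty is implied, since 9.4 exempts only what comes later and does not state the duty positively.

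**Step 2: width of the conflict.**

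- SAEs of any causality: 30 − 28 = 2 days (days 29 and 30).
- Related SAEs: from day 29 with no end date.

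**Step 3: the planned follow-up interval.** Inputs are Week 16 at 113 ± 3 (Protocol 7.7), Week 20 at 141 + 3 (Protocol 7.8) and dosing allowed on the Week 16 visit day (Protocol 7.7).

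- Nominal interval: 141 − 113 = 28 days, which reproduces the 4-week follow-up in Protocol 4.2.
- Week 16 range: 113 − 3 = 110 to 113 + 3 = 116. Week 20 range: 141 to 141 + 3 = 144.
- Shortest interval, last dose on the Week 16 visit day: 141 − 116 = 25 days.
- Longest interval: 144 − 110 = 34 days.
- The result is the same on the schedule-table day numbers and on the Section 7 text.

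**Step 4: how often the windows fall short.** There are 7 × 4 = 28 combinations of Week 16 and Week 20 days.

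- Below 28 days: 3 + 2 + 1 + 0 = 6 combinations (Week 20 on 141, 142, 143, 144 in turn).
- Below 30 days: 5 + 4 + 3 + 2 = 14 combinations.

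These count permitted combinations; they are not probabilities.

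**Step 5: sensitivity to the last-dose day.** If the last dose is the day before the Week 16 visit, the minimum is 141 − 115 = 26 days. If it is on Day 112 (16 × 7), the interval runs from 141 − 112 = 29 to 144 − 112 = 32 days. For early terminators, the call falls at 28 to 28 + 3 = 31 days.

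**The case against.** The strongest reply is that 9.5.5 limits data entry and leaves the duty to report intact. Section 9.4 still requires notification of related SAEs learned of after discharge, and a site can notify the sponsor without adding a record to the eCRF. This stands. A reader might infer that late serious events are lost to safety reporting; the documents do not support that. What they support is that such events can be absent from the eCRF. For SAEs known before discharge, the route in 9.5 and the bar in 9.5.5 still collide.

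Follow-up to resolution and a database cut-off are different duties, so 9.5.5 does not contradict itself on that point. This also stands. The consequence remains that the final outcome of an SAE ongoing at the last visit would not reach the eCRF.

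The 28-day line recurs in SAP 10.2, in pregnancy reporting (Protocol 9.6) and in the early-termination call (Protocol 7.9), so SAP 10.2 agrees with 9.5.5 on the day. It disagrees on related events.

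On timing, 25 days needs Week 16 three days late, a dose taken that day, and Week 20 on its target day. It is a permitted extreme. A reader might also infer that part of a promised 30-day surveillance period goes unobserved. The documents promise no such period: 30 days is a ceiling on reporting, and planned follow-up is 4 weeks. Events on days 26–28 are not barred; they may only lack a later scheduled contact.

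Protocol 9.4.4 leaves the details of AE entry to completion guidelines that are not among the documents. They may soften the problem in practice, but they should not have to override the protocol.

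**Conclusion.** The conflict is real and stands in the text. For SAEs of any causality it covers days 29 and 30; for related SAEs it runs from day 29 without limit. Following 9.5.5 as written would leave reportable SAEs, and late outcomes of ongoing ones, out of the eCRF-based safety tables. Timing of the last contact is a secondary matter: nominally 28 days, and 25 to 34 days if the last dose is on the Week 16 visit day.

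The conclusion rests on three assumptions: that the 30-day duty follows from the exemption in 9.4; that the AE summaries draw on the EDC, where Protocol 9.4 says AEs are collected; and that 9.5.5 is applied literally. The documents give no rate of late SAEs, so the number affected cannot be computed. It is probably small: Protocol 1.2 reports no related SAEs, with 458 participants having received EDP1815. The primary efficacy estimand is not touched. The point should be corrected, but it does not threaten the trial's main conclusion.

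**What to change.** Reconcile Protocol 9.4, 9.5 and 9.5.5 and SAP 10.2 to one post-dose window and one recording route. The documents do not show whether 28 or 30 days was intended, so the sponsor must decide and use the same limit throughout.

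Add an explicit exception to 9.5.5 so that three things are entered in the eCRF: SAEs that are reportable under 9.4, later events considered related, and outcome updates for SAEs ongoing at the end-of-study visit. Align the follow-up phase in SAP 5.3.4.2 with the result.

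Then check the agreed window against the last contact for completers who do not enter the open-label extension. If the Week 20 visit can fall before the window closes, a telephone check tied to the last dose, as early terminators already have, would cover the gap.

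The cost is amendment wording, a matching change to the eCRF completion guidelines and the SAP, and possibly an occasional telephone call. No new study procedures are needed.
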